Experimental Approach to the Problem

Research Design

Twenty-four to Thirty healthy, resistance-trained men (n=12-15) and women (n=12-15) between the ages of 18 and 35 will be recruited for this randomized, cross-over investigation. In order to be considered resistance trained, participants will need to have been engaged in resistance trained for ≥ 1 year prior to study enrollment and must be able to leg press at least 2x their bodyweight. Participants must also be free of any physical limitations, metabolic or cardiovascular disorders, and musculoskeletal injuries. Females will be excluded if they are not eumenorrheic and/or report the use of hormone-based contraceptives (e.g. oral contraceptive pill) within the previous 3 months. For female participants, all experimental sessions will take place within the same phase of their menstrual cycle. Furthermore, all participants will be asked not take any other nutritional supplements, performance enhancing drugs, and non-steroidal anti-inflammatory drugs (NSAIDs) throughout the duration of their enrolment in the study. Additionally, participants will be excluded if they have a history of antibiotics or intentionally consumed probiotics in the two months prior to enrollment in the study. If a participant has recently consumed probiotics, an 8-week washout period will be required before the participant is enrolled in the study. The study protocol will be approved by the Lipscomb University Institutional Review Board before participant enrollment.

Testing Procedures

Informed Consent & Questionnaires

Following an explanation of all study protocols, benefits, and risks, each participant will provide their written informed consent prior to participation in this study. Furthermore, participants will complete a PARQ2018+, health and activity questionnaire, food frequency questionnaire, and the Gastrointestinal Symptom Rating Scale (GSRS). The GSRS is an instrument of 15 items combined into five symptom groups representing Reflux, Abdominal pain, Indigestion, Diarrhea and Constipation. The GSRS has a seven-point graded Likert-type scale where 1 signifies absence of troublesome symptoms and 7 represents very troublesome symptoms. The reliability and validity of the GSRS has been previously established (3). The food frequency questionnaire will be used as an additional assessment tool for account for macronutrient and fiber intake when making gut composition comparisons.

Anthropometric & Body Composition Assessment

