Participants will be coached to maintain their usual dietary intake in the days preceding the acute resistance exercise trials. Throughout the 24 hours before first experimental trial, each participant will additionally be instructed to record everything they consume in a precise manner. To achieve this, each participant will meet with a registered dietitian for a brief education session to aid in accurate content, quantity, and timing of food in their logs. In subsequent trials, participants will be provided their first dietary log and asked to replicate the content, quantity, and timing of their daily diet during the 24 hours prior to the experimental trial in addition to recording everything they consume. Dietary recalls will be analyzed with the nutrition database, Nutritionix (Syndigo LLC, WA, US).

Stool Collection, Handling and Storage

Participants will be provided with a stool sample collection system during their first visit to the lab and instructed to collect a stool sample in the 24-48 hours prior to reporting for their second visit to the lab to complete the first study condition. Upon arrival to the lab, participants will provide the stool sample and investigators will subsequently aliquot and store samples at -80°C.

Resistance Exercise Protocol

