Experimental trials will be completed in a balanced, randomized order with each trial being separated by a minimum of one week to warrant adequate recovery. An overview of the acute resistance exercise protocols is presented in Figure 1. All experimental trials will also be performed within a 2-hour window to avoid diurnal variations. Ample hydration status will be verified (USG ≤ 1.020 defined as euhydration) via urine samples collected upon arrival to the HPL and analyzed for specific gravity (USG) by refractometry. During the exercise experimental trial, participants will perform the same standardized warm-up routine described earlier for 1RM testing, followed by either a resistance exercise protocol, consisting of the squat, seated shoulder press, deadlift, bent-over row, and leg press exercises. The exercise protocol will utilize a load of 70% 1-RM for 4 sets of 10 repetitions and a 90-second rest period length between sets and exercises. The control session will consist of participants completing assessments but will rest seated for 40 minutes instead of exercising. Treatment order (control or exercise) will be randomized using a random number generator. A similar exercise protocol has been demonstrated to significantly elevate I-FABP, a marker of gut permeability (25). During each protocol, if the participant is unable to complete the desired number of repetitions, spotters will provide assistance until the subject completes the remaining repetitions. Immediately upon completion of the acute resistance exercise bout, participants will complete IP assessments.

[figure not shown]

Figure 1. Acute Resistance Exercise Protocol Overview. PRE = Pre-exercise; IP = Immediately-post exercise. RE = Resistance Exercise; GI = Gastrointestinal; 1RM = 1-Repetition Maximum

Acute GI Distress Questionnaires

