mL water. Saccharide concentrations will then be determined from serum samples at all time-points and the LR ratio will be calculated. Serum will be analyzed for endotoxin concentration using a commercially available kinetic limulus amebocyte lysate (LAL) assay (Lonza; Allendale, NJ). Circulating plasma concentrations of the pro-inflammatory cytokine TNF- α will be assayed via commercially available ELSIA kits (ALPCO, Salem, NH, USA).

For fecal analysis, feces will be thawed, and 100 mg will be added to 4.9 ml of extraction buffer (0.1 M Tris, 0.15 M NaCl, 1.0 M urea, 10 mM CaCl₂ 2H₂O, 0.1 M citric acid, 0.5% BSA, pH 8.0). After 30 minutes shaking, 1 ml of suspension will be centrifuged at 10,000 rpm for 20 minutes at 4°C. Fecal supernatants will be assayed for calprotectin via ELISA (Eagle Biosciences, Nashua, NH) using manufacturer's instructions. A summary of the markers of interest is presented in Table 1.

Table 1. Biochemical Markers of Interest

Marker	~24H Pre	Pre	IP	15min	30min	60min	~24H Post
Blood							
I-FABP	X	X	X	X	X	X	
Endotoxin (LAL)	X	X	X	X	X	X	
Lactulose/Rhamnose Ratio	X	X	X	X	X	X	
Fecal							
Shallow Shotgun Metagenomics	X						
SCFA	X						

I-FABP = Intestinal Fatty-acid Binding Protein, LAL = limulus amebocyte lysate, SCFA = Short-Chain Fatty Acids. 24H Pre= 24hours before exercise, Pre= Pre-exercise, IP = Immediately post-exercise, 24H = 24-hours post-exercise.

Fecal Shallow Shotgun Metagenomics

After collection, 10-20g feces will be separated into sterile collection containers and immediately frozen at -20°C. After thawing, DNA will be extracted from samples using the Qiagen MagAttract PowerSoil DNA KF Kit (formerly MO BIO PowerSoil DNA Kit) optimized for the ThermoFisher KingFisher robot according to manufacturer's instructions. Whole DNA will be prepared for sequencing using the Illumina Nextera Flex DNA library prep kit. Samples will be barcoded and mixed together for sequencing. The mix will then be subjected to paired-end sequencing using Illumina sequencers. Paired reads will be concatenated and processed to remove adaptors, barcodes and low-quality reads as well as contaminant sequences (typically host DNA). Sequences will then be mapped to databases to obtain taxonomic and functional profiles. Sequencing will be performed on the Illumina NextSeq. The number of reads targeted ranges from 0.5 to 3 million.

Fecal Short-Chain Fatty Acid Analysis

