Prior to analysis all data will be assessed to ensure normal distribution, homogeneity of variance and sphericity. Non-normally distributed data will be transformed using the natural log (LN) and if sphericity is violated, a Greenhouse Geisser correction will be applied. General Linear Model (GLM) repeated measures analyses [time x trial x sex] will be used to compare trials (RE, CON) for all variables. Following a significant F ratio, separate one-way repeated-measures ANOVA will be performed to assess the effect of time during each trial, and separate paired-samples t-tests will be used to compare trials at each time point. Separate independent t-tests will also be used to evaluate specific differences between sexes when applicable. An alpha level of $p < 0.05$ will be considered statistically significant for all comparisons. Based on a standard deviation of $511 \text{ pg}\cdot\text{ml}^{-1}$ and $347 \text{ pg}\cdot\text{ml}^{-1}$ for post-exertional I-FABP for males and females, respectively (8) and using a standard alpha (0.05) and beta value (0.8), a sample size of $n= 4$ per group was calculated to have adequate statistical precision to detect a $> 110\%$ increase in I-FABP post-exercise. Such increases in I-FABP after exercise have also been correlated with the magnitude of intestinal permeability (9). Current participant numbers are also in accordance with sufficient statistical precision to detect significant differences in gastrointestinal symptoms (1). From the metagenome sequencing the group comparisons of gut microbiota will be analyzed with non-parametric Wilcoxon matched-pair signed rank test and corrected for multiple comparison with Benjamini-Hochberg procedure. Regarding the taxonomic data, all analyses will be made with Quantitative Insights Into Microbial Ecology (QIIME) open-sourced software from the randomly subsampled Operational Taxonomic Unit (OTU) table with rarefaction level matching the sample with the lowest total OTU count. The bacterial diversity of the samples (α -diversity metrics) and statistically significant differences in the OTU abundances will be computed with QIIME. Any correlations between non-normally distributed gut microbiota and other variables will be determined using Spearman's rank correlation coefficient in SPSS. The GLM in SPSS will be used to determine whether differences in taxa occur due to biological sex or whether they are dependent on age, weight, body fat %, total energy intake, macronutrient composition, or fiber.

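### The microbiota group comparisons are assigned a matched-pair signed-rank test, but the sampling plan yields one stool sample per person and defines no pairs

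*Protocol*

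**What the plan says.** Three parts of the protocol bear on this.

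- **Statistical Analysis, the test.** "group comparisons of gut microbiota will be analyzed with non-parametric Wilcoxon matched-pair signed rank test", with Benjamini-Hochberg for multiplicity. The sentence does not say which groups are compared.
- **Stool Collection, Handling and Storage, the data.** Each participant is to "collect a stool sample in the 24-48 hours prior to reporting for their second visit to the lab to complete the first study condition". No collection is described for the third visit or after either session. In Table 1 the row "Shallow Shotgun Metagenomics" carries a single mark, in the column for about 24 hours before, and none in the column for about 24 hours after. The short-chain fatty acid row is the same.
- **Research Design and Statistical Analysis, the possible groups.** The trial enrols 12 to 15 men and 12 to 15 women, with no matching rule. A later sentence of the Statistical Analysis section uses a general linear model to "determine whether differences in taxa occur due to biological sex" or depend on listed covariates such as age, body fat and fibre. For sex differences in other variables, the same section uses independent-samples t-tests.

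**The concern.** A signed-rank test works on within-pair differences, so it has no input unless each observation has a defined partner. Here each person contributes one microbiota profile, and men and women are separate people with no matching. An analyst who follows the text would have to invent a pairing, for instance by file order, or depart from the protocol.

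At stake is the taxon-by-taxon comparison to which the Benjamini-Hochberg correction is attached. It could not be reproduced by a second analyst, and it might not be computable at all.

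**Working it through.** The protocol gives no power or sample-size figure for the microbiota comparison, so there is nothing to reproduce. The check is a count of pairs, followed by an illustrative simulation.

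**Step 1: count the pairs**

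- Exercise versus control, within person: this needs stool at both conditions. The stool section places the only sample before the first condition. Pairs available: 0.
- Before versus after exercise, within person: this needs a post-exercise sample. None is described. Pairs available: 0.
- Men versus women: this needs a matching rule. None is described. Pairs defined: 0.

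**Step 2: unequal groups**

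Any split from 12 to 15 per sex is allowed. With 12 of one sex and 15 of the other there are 12 + 15 = 27 people, at most 12 pairs, and 15 − 12 = 3 people left over (3/27 = 11%).

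**Step 3: equal groups, paired at random**

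Assumptions, none from the protocol: normal data with SD 1, two-sided 0.05, 4,000 runs. The entries are rejection rates.

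| n per sex | True difference | Signed-rank, arbitrary pairs | Rank-sum |
|---|---|---|---|
| 12 | 0 | 0.038 | 0.046 |
| 12 | 1 SD | 0.56 | 0.60 |
| 15 | 0 | 0.041 | 0.042 |
| 15 | 1 SD | 0.71 | 0.73 |

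Random pairing does not raise the false-positive rate. It costs a little power.

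**Step 4: dependence on the pairing**

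Twelve men and twelve women can be paired in 12! = 479,001,600 ways. In one simulated 12 versus 12 dataset, the signed-rank p-value ran from 0.034 to 0.85 over 5,000 random pairings. The rank-sum test gives one answer for those data, p = 0.58. Only about 0.1% of those pairings fell below 0.05, so the low end was rare in that dataset.

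Over many datasets (log-normal abundances, 12 versus 12, 300 datasets), the share in which some pairings gave p < 0.05 and others did not was:

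| Pairings tried | No difference | Shift of 0.8 log-SD |
|---|---|---|
| 5 | 7% | 31% |
| 20 | 16% | 52% |
| 60 | 21% | 61% |
| 200 | 30% | 66% |

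Other runs at 60 pairings gave 17% to 24% with no difference and 59% to 62% with the shift, depending on scale and run. These shares grow with the number of pairings tried. They show that the decision can move, and they are not error rates.

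**The case against.** Four objections deserve an answer.

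1. **The sentence does not say men versus women.** This stands. A reader might infer that the protocol states a sex comparison here; it does not. The groups are undefined, and sex is what the sampling plan and the later model sentence leave. No other reading supplies the pairs either.
2. **Table 1 may describe each session.** This stands in part. Its columns are times around one session, and the blood markers too have one row for two trials, so a single mark does not by itself prove a single sample. The stool section does limit collection to the time before the first condition. Even if a sample were taken before each trial, each would precede its own session and would not measure the response to it.
3. **The p-values are not arbitrary.** This stands. A reader might infer inflated false positives, or results driven by row order instead of data. Neither is supported. In the log-normal simulation the null rejection rate was 5.2%, and power at the 0.8 shift was 0.41 against 0.47 for rank-sum. An arbitrary pairing reached the rank-sum decision about 96% of the time with no difference and 85% with the shift.
4. **Sex is analysed elsewhere.** This stands. The same section gives the linear model with covariates and also says that differences in taxonomic abundance will be computed in QIIME. A reader might infer that the protocol has no usable analysis of sex and taxa; that goes too far. Only the Wilcoxon step and its multiplicity correction are affected.

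The point is not one to leave to a statistical analysis plan. The protocol names a test, and its own sampling plan cannot supply the data for it.

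**Conclusion.** Wrong as written. The named test has no pairs to work on: none within person, and none defined between men and women. The apt description is not applicable, since random pairing holds its nominal level. The consequences are that the test cannot be run on unequal groups without discarding people (3 of 27 at 12 versus 15), and that with equal groups the p-values and the list of taxa passing Benjamini-Hochberg depend on a pairing that nobody has specified.

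The conclusion rests on the stool section, which describes one sample per participant, and on the absence of any matching rule. It does not rest on the simulations, whose effect sizes, distributions and numbers of pairings are assumptions. The exercise-versus-control comparisons of the blood markers and the sample-size statement for I-FABP are not touched.

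**What to change.** Amend the sentence in the Statistical Analysis section to say that the microbiota group comparison is men versus women, tested per taxon with the Wilcoxon rank-sum (Mann-Whitney) test and corrected by Benjamini-Hochberg, alongside the covariate-adjusted linear model already planned. The rank-sum test accepts unequal groups and gives one result per taxon.

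This costs one sentence, with no extra data and no burden on participants. No other outcome in the section is assigned the signed-rank test, so nothing else needs changing.

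If a within-person comparison was intended, state which two samples are compared and add the second one, with its timing, to the stool section and to Table 1. That costs a further collection and sequencing run per participant. It has to be settled before participants complete their visits, because a missed sample cannot be recovered.

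### The Spearman correlations of gut microbiota with other variables make no allowance for sex, so a sex difference in both variables can appear as an association

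*Protocol*

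**What the plan says.** The Statistical Analysis section of the Protocol fixes one method for these associations: "Any correlations between non-normally distributed gut microbiota and other variables will be determined using" Spearman's rank coefficient, run in SPSS. It gives no sex term, partial coefficient or separate analysis for men and women. It does not list the other variables. The significance level is 0.05, which "will be considered statistically significant for all comparisons"; sidedness is not stated.

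The sample in Research Design is "Twenty-four to Thirty healthy, resistance-trained men (n=12-15) and women (n=12-15) between the ages of 18 and 35", so about half are of each sex. Under Stool Collection, participants are "instructed to collect a stool sample in the 24-48 hours prior to reporting for their second visit to the lab". That is one sample, and so one value per taxon, per person. The plain reading is one coefficient per taxon-variable pair across all 24-30 people.

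Sex does enter two other analyses in the same section:

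- The trial comparison: "General Linear Model (GLM) repeated measures analyses [time x trial x sex] will be used to compare trials (RE, CON) for all variables".
- A model of the taxa: "The GLM in SPSS will be used to determine whether differences in taxa occur due to biological sex or whether they are dependent on age," followed by weight, body fat percentage, total energy intake, macronutrient composition and fiber.

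**The concern.** The Protocol treats sex as a possible source of difference in the outcomes (first model) and in the taxa (second model). Those are the two sides of the planned correlations, yet the correlation itself takes no account of sex. Where both sides differ by sex, men cluster in one corner of the scatter and women in the opposite one. The overall ranks are then correlated even if, among men and among women, the taxon says nothing about the marker.

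A reported link between a taxon and, say, I-FABP could then be two sex differences restated as one association. Sex gaps that run against a real within-sex association could also weaken it. This is confounding, so a multiplicity correction of the p-values would not remove it.

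**Working it through.** **Plan's own figure.** There is none to reproduce. The Protocol gives no power, error rate or expected coefficient for the correlations, and its n = 4 per group concerns I-FABP only.

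**Inputs.**

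- From the Protocol: 12+12 to 15+15 participants, one taxon value each, alpha 0.05.
- Assumed: a two-sided test; zero correlation within each sex; sex gaps of d1 SD in the taxon and d2 SD in the other variable. The Protocol gives no sex-specific means. Its only sex-specific figures, 511 and 347 pg/ml for I-FABP, are standard deviations.

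**Step 1: expected size of the spurious correlation.** With half of each sex and unit within-sex variance, a gap d adds d²/4 to a variable's variance, and the two gaps add d1·d2/4 to the covariance. On the raw scale:

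r = (d1·d2/4) / √[(1 + d1²/4)(1 + d2²/4)]

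- d1 = d2 = 0.5: 0.0625/1.0625 = 0.059
- d1 = d2 = 0.8: 0.16/1.16 = 0.138
- d1 = d2 = 1.0: 0.25/1.25 = 0.200
- d1 = 0, any d2: 0

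**Step 2: simulation.** 20,000 data sets per setting, normal variables. Because Spearman uses ranks, a monotone transformation such as a log changes nothing. The unadjusted test uses t = ρ√[(n−2)/(1−ρ²)] on n−2 df. The sex-partial test ranks each variable over everyone, subtracts the mean rank of the person's own sex, correlates the remainders, and uses t = ρ√[(n−3)/(1−ρ²)] on n−3 df.

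| Gap in taxon / other variable (SD) | Mean unadjusted ρ | Unadjusted rejection, 12+12 / 15+15 | Sex-partial rejection, 12+12 / 15+15 |
|---|---|---|---|
| 0 / 0 | about 0 | 5.1% / 5.1% | 4.9% / 5.1% |
| 0 / 1.5 | about 0 | 4.8% / 5.0% | 4.8% / 5.0% |
| 0.5 / 0.5 | 0.06 | 6.1% / 6.1% | 5.2% / 4.9% |
| 0.8 / 0.8 | 0.14 | 10.1% / 10.7% | 5.0% / 5.0% |
| 1.0 / 1.0 | 0.21 | 16.2% / 19.2% | 4.9% / 5.0% |

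The mean ρ agrees with Step 1. Unequal standard deviations alone (511 against 347, 12+12) give 5.0%, so the I-FABP spreads in the Protocol cause no inflation by themselves.

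**Step 3: hand check of the 1 SD row.** Fisher's z of 0.200 is 0.203.

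- n = 24: 0.203 × √21 = 0.93; P(Z > 1.96 − 0.93) + P(Z < −1.96 − 0.93) ≈ 0.15
- n = 30: 0.203 × √27 = 1.05; the same sum ≈ 0.18

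Both are close to the simulated 16% and 19%.

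**Step 4: cost of adjusting when it is not needed.** With a within-sex correlation of 0.6 and no sex gaps, power falls from 85.0% to 83.3% at N = 24 and from 92.5% to 91.5% at N = 30.

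**The case against.** **The analysis is nowhere called pooled.** True. It is inferred from the absence of any stratification, and a statistical analysis plan that is not shown could stratify. But the Protocol names a specific procedure, and that procedure as written contains no sex term. This limits how firmly the point can be put, but does not remove it.

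**The taxa GLM already deals with sex.** This stands in part. That model sets sex beside age, weight, body fat, energy, macronutrients and fiber. A reader might infer that the defect is worst for body fat, since a 2 SD sex gap there with 1 SD in the taxon would give 36-45% rejection. The documents do not support using that example: the gap is assumed, and body fat is a covariate already considered with sex. I-FABP, lactulose/rhamnose ratio, endotoxin, TNF-alpha, calprotectin, short-chain fatty acids and symptoms are not in that model. The trial-comparison GLM includes sex but compares exercise with control; it does not test taxon-marker associations.

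**An overall coefficient is a legitimate description.** This also stands. Spearman's null is independence in the mixed sample, and a rejection caused by sex is correct against that null. The Protocol does not say that a within-sex association is the target. The overall coefficient cannot, however, serve as evidence of a link apart from sex, which is how a taxon-marker correlation would usually be read.

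**No sex gap is documented.** Correct. The Protocol asks whether taxa differ by sex; it does not say that they do.

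**Conclusion.** The point holds conditionally. As written, the microbiota correlations are open to confounding by sex in a sample that is about half men and half women. The exposed correlations are mainly those of taxa with the gut-damage, permeability, inflammation, short-chain fatty acid and symptom measures.

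The size depends on assumed gaps in both variables: negligible at 0.5 SD (about 6% against 5%), about double the nominal rate at 0.8 SD (10-11%), and three to four times it at 1 SD (16-19%). It is nil if only one variable differs.

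A reader might go further and conclude that the plan produces false microbiota associations. The documents do not support that, because they give no sex difference in the mean of any taxon or marker. These are secondary correlations, and neither the sample size nor the exercise-control comparison rests on them. This is a cheap improvement that should be made, not a fault that undermines the trial.

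**What to change.** Amend the sentence on correlations in Statistical Analysis. For taxa against variables outside the taxa GLM, base inference on a Spearman correlation partialled on sex: rank both variables over all participants, centre the ranks within sex, correlate, and test on n−3 df. Show the coefficients for men and for women beside it as a check on consistency; with 12-15 people each they will be imprecise. Keep the unadjusted coefficient as descriptive and label it so.

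The cost is a sentence or two of wording, one degree of freedom, and about 1-2 points of power when there is no sex difference. No further participants, samples or visits are needed.
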